#### **11.4.4 Secondary outcome analysis**

The key secondary endpoint is the timing of recovery (defined as the time necessary to cover the minimal age- and sex-specific normal distance in meters during the six-minute walk test AND the time necessary for foot drop to recover to a MRC-score  $\geq 4$  for ankle dorsiflexion). However, the study will be only powered for the primary endpoint but if the primary endpoint should show a significant difference, it is anticipated that also the timing of recovery might yield a significant effect. Motor strength will also be assessed at the following time points: at 6 weeks, 3 months, 6 months and 9 months. The time of recovery will be analysed using a generalized log-rank test with constant weights over time for interval-censored data. In addition, the Turnbull estimator with 95% confidence intervals will be produced. The estimated proportion of patients which are recovered will be estimated at 6 weeks, 3 months, 6 months and 9 months. We do not anticipate any mortality due to the pathology. In case a patient should die, the patient will be censored at his day of death.

Full details on the analysis of the key secondary endpoint and the analysis of the other secondary endpoints will be described in the SAP.

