The endpoints will be evaluated at fixed time-points: 6 weeks, 3 months, 6 months and 9 months after randomization. Extended follow-up is scheduled 9 months after the primary endpoint is reached i.e. 18 months after randomization. Most trial assessments will be performed by the site-specific blinded researcher, ideally an independent physiotherapist. Patients allocated to the surgical arm of the trial will be evaluated 10 days after neurolysis. A postoperative control is considered standard of care. Sensorimotor function, quality of life and complications will be assessed during this postoperative control. Assessment of MRC-scores for ankle dorsiflexion and ankle eversion is considered standard of care and shall be performed by the treating physician. The treating physician can also assess ankle dorsiflexion strength measured by isometric dynamometry. This cannot be done by the outcome assessor because this would lead to unblinding.

A list of standard assessments (clinical records, considered daily practice = SOC; including motor and sensory function, ability to walk (barefoot), need for orthosis, treatment) will be composed for uniformity across centers. Standard assessments will be conducted at each study visit.

Cross-over is not allowed until the primary endpoint at 9 months is assessed. After the primary endpoint is assessed, cross-over from the conservative arm to surgery is allowed and patients will be treated according to standard of care (decision between treating physician and patient). Extended follow-up for all patients will be organised, 18 months after randomization. All primary and secondary endpoints, with the exception of electrodiagnostics, WPAI and return to work, will be assessed at 18 months. The End-of-Study (EOS) visit will take place at 18 months post-randomization. Cross-over patients will be followed-up as per protocol. All participating physicians and trial sites have the responsibility to guide patients throughout the study visits and are expected to follow protocol and to inform patients in a correct, objective manner. If the TSC documents an unusual high percentage of cross-over in a specific trial site, this trial site can be excluded from the foot drop trial.

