The 6MWD will be evaluated twice at each visit (as first and last assessment), taking the 'learning effect' into account. Furthermore, the applied reference values are based on repeated 6MWD. Best 6MWD will be documented in the eCRF.

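### Censoring deaths on the day of death does not fit the interval-censored analysis of time to recovery: for patients who die without documented recovery, it counts unobserved time as known non-recovery

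*Protocol*

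**What the plan says.** Section 11.4.4 of the protocol fixes the method for the key secondary endpoint: "The time of recovery will be analysed using a generalized log-rank test with constant weights over time for interval-censored data". It adds: "In addition, the Turnbull estimator with 95% confidence intervals will be produced". Recovered proportions are to be estimated at 6 weeks and at 3, 6 and 9 months.

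Recovery needs two things: a walking distance at or above the age- and sex-specific minimum, and an MRC score of at least 4 for ankle dorsiflexion (Sections 4.3.2 and 8.7.1). Both depend on visits. Section 5.1 states: "The endpoints will be evaluated at fixed time-points: 6 weeks, 3 months, 6 months and 9 months after randomization". Section 11.4.4 says of the motor component: "Motor strength will also be assessed at the following time points: at 6 weeks, 3 months, 6 months and 9 months". The walk test is also done only at visits (Sections 8.7.5 and 8.8). The 10-day postoperative check includes an MRC score but no walk test, so it cannot establish recovery.

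On mortality, Section 11.4.4 says "We do not anticipate any mortality due to the pathology" and then gives the rule: "In case a patient should die, the patient will be censored at his day of death". Full details of the analysis are left to the SAP. Nothing in the protocol provides for an assessment of either criterion at or near death.

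**The concern.** Right-censoring at the day of death suits an event whose time is seen as it happens: if it had not been seen by that day, it had not happened. Recovery here is not observed in that way. A patient unrecovered at 3 months who dies at 5 months may or may not have recovered in between, and nobody checked.

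The interval that matches the data is (last assessment, infinity). The stated rule gives (day of death, infinity), which claims non-recovery over the time between. That conflicts with the reason for choosing a method "generalized log-rank test with constant weights over time for interval-censored data". The error has a direction: it tends to lower the estimated recovery curve of the arm in which the death falls. At stake is a small, avoidable bias in the key secondary analysis.

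**Working it through.** **Plan's own figure.** The point depends on no stated figure. For completeness, the sample size reproduces: an effect size of 0.5, two-sided 5% and 90% power with a t-test need 85.03, so 86 per arm, or 172. Then 172 / 0.95 = 181.05, which gives 182 (91 per arm). Nothing below changes it.

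**Length of the unobserved time.** Visits at 6 weeks and 3, 6 and 9 months are about weeks 6, 13, 26 and 39, so the gaps are 6, 7, 13 and 13 weeks. A death just before the next visit adds up to about 13 weeks of unobserved non-recovery, and more if a visit was missed.

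**Assumed arm.** The protocol gives no recovery or death rates, so these are assumptions. Take 91 patients with one death and 90 others: 18 recover in each of weeks 0-6, 6-13 and 13-26, 14 in weeks 26-39, and 22 remain unrecovered at week 39. The Turnbull estimate then has a closed form at the visit times. By week 13 it is 36/91 = 0.396, and 55 patients remain (18 + 14 + 22 + 1 death).

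*(a) Nominal dates, no missed visit. Death at week 25, last visit week 13.*
- Last-visit coding (13, infinity): estimate at week 26 = 36/91 + (55/91)(18/54) = 0.597.
- Day-of-death coding (25, infinity): recovery in weeks 25-26 is still possible for this patient, so the estimate is again 0.597.
- The only change lies inside the gap. The mass of 0.20 that the data place somewhere in weeks 13-26 is forced into weeks 25-26.
- An interval-censored log-rank test on two assumed arms of 91, with 1 or 3 deaths in one arm at week 7, 20, 25 or 35, gave the same statistic under both codings (for example z = 2.1549 both ways for one death at week 20). No other patient's interval ends between the last visit and the death.

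*(b) Missed 26-week visit. Last visit week 13, death at week 30.*
- Day-of-death coding: the patient is fixed as unrecovered at week 26, so the estimate is 54/91 = 0.593.
- Last-visit coding: 36/91 + (55/91)(18/54) = 0.597. Difference: 0.4 points.
- Two such deaths (89 others: 18, 18, 18, 13 and 22): 54/91 = 0.593 against 36/91 + (55/91)(18/53) = 0.601. Difference: 0.7 points.
- Five such deaths (86 others: 17, 17, 17, 13 and 22): 51/91 = 0.560 against 34/91 + (57/91)(17/52) = 0.578. Difference: 1.8 points.

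*(c) Visits spread over their windows.* Simulated arms of 91, exponential recovery with 75% recovered by week 39, visits up to 1 week late (6 weeks) or 2 weeks late (3, 6 and 9 months), and 80 data sets per row. The entries are the mean change in the recovered proportion, day-of-death minus last-visit coding, in percentage points:

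| Assumed deaths over 9 months | Week 8 | Week 15 | Week 28 | Week 41 |
|---|---|---|---|---|
| 1% (0.9 per arm) | -0.10 | -0.16 | -0.11 | 0.00 |
| 5% (4.6 per arm) | -0.49 | -1.19 | -0.52 | -0.08 |
| 10% (9.1 per arm) | -0.86 | -2.22 | -1.25 | -0.11 |

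Further fits with visits spread over the windows gave an average shift of about 0.1 points for one death and 0.5 points for three, with occasional larger shifts in single data sets.

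**How many deaths to expect.** 182 x 0.75 years = 136.5 person-years. At an assumed all-cause mortality of 0.5% to 2% per year this gives 0.7 to 2.7 deaths in the whole trial. Only those without documented recovery count.

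**The case against.** The best defence has three parts.

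First, the sentence may mean only that death ends follow-up and is not an event, with the coding of intervals left to the SAP. This reading is possible but not the natural one. The text names a date, and a programmer would enter that date. The protocol therefore states a rule here; it does not leave a gap. A SAP that follows it inherits the error, and one that corrects it departs from the protocol.

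Second, the rule often changes nothing that is reported. This stands: in case (a) the test and the estimates at the planned times are identical. A difference needs visit dates that vary or a missed visit. Varying dates are to be expected, because the schedule in Section 8.8 allows windows.

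Third, deaths will be few, and the endpoint is secondary and not powered. This also stands and limits the weight of the point.

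Two stronger readings are tempting. A reader might infer that every death before 9 months is misstated. It is not: a patient with documented recovery keeps a closed interval between two visits, whatever happens later. A reader might also infer that the same rule governs withdrawals and losses to follow-up, since it is the only censoring rule in the section. The sentence covers death alone, and Section 11.4.5 leaves missing data to the SAP, so the protocol does not support that extension.

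**Conclusion.** The rule is wrong as written for one group: patients who die without documented recovery. For them it treats unobserved time as known non-recovery, against the logic of the method named in the same paragraph, and it biases towards later recovery.

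The size is small. It is zero at the nominal visit times when visits are on schedule and none is missed. With visits spread over their windows it is on average well under 1 percentage point for up to three deaths per arm. It passes 1 point only in less likely settings, such as an assumed 5% mortality over nine months or several deaths that each follow a missed visit. These sizes rest on assumed recovery and mortality rates; the direction and the mismatch with the method do not. Which arm the bias favours depends on where the deaths fall. The primary analysis and the total of 182 patients are not affected. This is a minor correction, worth making because it is free.

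**What to change.** Replace the sentence on deaths in Section 11.4.4 by: *A patient who dies without documented recovery is right-censored at the last visit at which the recovery criteria were assessed and not met; a patient with documented recovery before death keeps the observed interval.* Carry the same wording into the SAP. The cost is one sentence in each document. No extra data, visits or patients are needed, and no planned figure changes.

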#### **11.4.5 Procedure(s) to account for missing or spurious data**

Real time data checks will be built into the data collection tool (eCRF) and further data management queries including missing data, out of range values, will be emailed to the centres on a regular basis, in accordance with the data management plan. Outstanding data queries will be reviewed on a regular basis by the trial coordinating and data management teams. Feedback will be provided to all centres on a regular basis.

Protocol deviations will be reviewed and classified (major/minor) on a regular basis by the trial co-ordinating team and will be escalated if recurring issues emerge. Major deviations will be flagged to the trial statistician and the trial Sponsor.

The handling of missing data will be described in the statistical analysis plan (SAP).

#### **11.4.6 Other statistical considerations.**

The analysis of the economic evaluation will be described in a separate analysis plan.

### **11.5 Data collection for economic evaluation**

One of the goals of the KCE Trials programme is to improve the efficiency of the healthcare system. This protocol has been designed with a later possible economic analysis in mind. The economic analysis itself is however not part of this protocol. Several characteristics of the foot drop trial make an economic analysis more feasible(117):

- a. During the foot drop trial, there will be protocol-driven resource use that will bias costs in both treatment groups. There will be more hospital visits and technical investigations (EDX) than in standard of care. However, these extra costs are the same in both treatment arms and these costs are known. Bias will be very limited.
- b. The comparator (prolonged conservative therapy) is relevant and considered daily practice.
- c. We expect the recruiting centers to be representative of the larger population, given the large number of participating centers.
- d. Compliance is not artificially enhanced.
- e. The trial is designed to be naturalistic and to evaluate the effectiveness of interventions in real-life routine practice conditions.

Participation of Dutch centers can complicate economic analyses, since costs can differ substantially between different health care systems.

In a recent review Poage et al. (1) state that if a peroneal neuropathy is not treated properly the percentage of people with permanent motor weakness ranges from 30 to 35 %. The percentage of invalidity for a complete paralysis of the peroneal nerve is estimated at 22 % (European physical and mental disability rating scale for medical purposes ([https://www.ecb.europa.eu/careers/pdf/annex\\_II\\_staff\\_rules\\_ft.pdf](https://www.ecb.europa.eu/careers/pdf/annex_II_staff_rules_ft.pdf))). De Bruijn (118) et al. reported on the economic impact of peroneal neuropathy in 19 patients. Nine of these patients (47%) with a paid job experienced some restrictions in work. Work adaptations were reported by two patients. No jobs were lost because of the nerve injury. In the OBSI (*officiële Belgische schaal ter bepaling van de graad van invaliditeit*), the acknowledged percentage of invalidity due to severe limitations in ankle dorsiflexion (and/or plantar flexion) is 10 to 20% ([http://www.ejustice.just.fgov.be/cgi\\_loi/change\\_lg.pl?language=nl&la=N&cn=2006020831&table\\_name=wet](http://www.ejustice.just.fgov.be/cgi_loi/change_lg.pl?language=nl&la=N&cn=2006020831&table_name=wet)). During the pilot trial, the foot drop trial will assess the feasibility of documenting the percentage of invalidity, acknowledged by health care insurances.

Health-related Quality of Life data will be collected in both trial arms at baseline, 10 days, 6 weeks, 3 months, 6 months, 9 months and 18 months. Cost-effectiveness will be calculated as cost per quality-adjusted life-year (QALY) gained. Cost and utility impact will be derived from the analysis of individual patient data. Since peroneal neuropathy represents a common neuropathy and people with a permanent motor deficit will suffer from gait abnormalities (with the need for an orthosis and physiotherapy), as well as

chronic pain and possible skin problems due to sensory and autonomic deficits, we believe that this condition will have an important impact on quality of life. In addition to quality of life measures, the work productivity and impairment questionnaire (WPAI) will be used to assess employment and professional productivity. The WPAI will be collected at baseline, 6 weeks and 6 months. The professional occupation of patients will be collected as baseline data. Return to work will be assessed six weeks after randomization. We expect patients to be able to return to work after improvement (of recovery) of foot drop. Relapse of foot drop is not expected in the majority of cases (see also Section 8.7.16).

The proposed trial will provide the ideal opportunity to collect data about quality of life, surgical complications, employment and professional productivity in patients with a foot drop due to peroneal nerve entrapment. In addition, these data will provide further insights into the quality of life of people with a foot drop resulting from other aetiologies (such as lumbar disc herniation), and even about patients with other entrapment neuropathies.

The economic evaluation will be conducted from a healthcare payer (base case) and societal perspective. The aim of the economic evaluation is to measure, value and analyse total costs of patients in both groups and to relate the difference in costs between the two treatment groups to the difference in clinical effects. The time horizon of the economic evaluation is 18 months, after collection of all clinical data that can be used for the cost evaluation of the intervention. Sensitivity analysis will be performed to assess the robustness of the results using different assumptions regarding costs and effects.

Effect measures in the economic evaluation will be calculated by the available QOL-questionnaires (EQ-5D 5L at baseline, 6 weeks, 3 months, 6 months, 9 months and 18 months). EQ-5D 5L is a sensitive QOL instrument in this trial, since mobility is one of the five dimensions of the EQ-5D 5L questionnaire. Therefore, we expect differences in outcome to be reflected in differences in EQ-5D 5L. EQ-5D 5L value sets are expected to be available at the end of the trial. If not, the EQ-5D-5L Crosswalk Index Value Calculator can be used. We expect to see a higher QOL for the surgical management of the foot drop.

To facilitate a later cost-utility analysis, quality of life data is collected during the trial (EQ-5D 5L). After the completion of the study the Sponsor will transfer the pseudonymised study data set to KCE. KCE will request approval from the competent chamber of the Information Security Committee (ISC) to have the relevant study data linked with e.g. IMA data by a trusted third party (TTP, eHealth platform) using the patient national number (see also 14.10 access to the study data by KCE and similar institutes in the EU).

This will allow to know the exact costs in both treatment arms, in which an important difference is to be expected. These costs are the costs of surgery, anaesthesia and hospitalisation in the surgical arm of the trial and costs of physiotherapy (F-pathology) in the conservative (and surgical) trial of the arm. The exact number of physiotherapy sessions will be recorded for all participants (treatment record). The costs of a foot-ankle orthosis will be documented as well (need for ankle-foot orthosis). If there is an unforeseen severe surgical complication, leading to hospitalization, these costs can be retrospectively determined through the national number of the patient. Other anticipated health care expenses are general practitioner care, costs of visits to other primary care providers, ambulatory and inpatient hospital care, medication and home care. The expected difference in these costs are expected to be relative minor and some of them are difficult to determine (home care), therefore, the economic analysis will not focus on these costs. Indirect costs include absenteeism from paid and unpaid work and presentism.

The incremental cost (ICER) will be calculated by dividing the difference in total costs between the treatment groups by the difference in mean effects (QOL) to compare both treatments.

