##### Other Secondary outcomes

1. **Ankle dorsiflexion strength:** measured by the MRC-score and isometric dynamometry at 10 days, 6 weeks, 3 months, 6 months, 9 months and 18 months after randomization. Ankle dorsiflexion strength will also be assessed after 10 days in the surgical arm of the trial.
2. **Gait assessment** at 6 weeks, 3 months, 6 months, 9 months and 18 months after randomization with
  - a. Functional ambulation categories, Stanmore questionnaire
  - b. Gait speed during the 10-meter walk test
  - c. The proportion of patients in both groups who reach minimal normal age- and sex-specific reference values for 6MWD, 9 months after randomization.
  - d. Difference in distance covered in meters during the six-minute walk test between baseline and 6 weeks, 3 months, 6 months and 18 months after randomization
3. **Complications and neurological deficits :**
  - a. Motor changes including MRC-score for ankle eversion and hallux extension at 6 weeks, 3 months, 6 months, 9 months and 18 months after randomization. Motor function will also be assessed after 10 days in the surgical arm of the trial.
  - b. Sensory changes at 6 weeks, 3 months, 6 months, 9 months and 18 months after randomization. Sensory changes will also be assessed after 10 days in the surgical arm of the trial.
  - c. Surgical complications at 10 days, 6 weeks and 18 months after surgery: a list of possible complications is composed to score in a uniform way in all centers.
4. **Health-economic assessment:**
  - a. Work productivity and Activity Impairment Questionnaire at 6 weeks and 6 months after randomization.
  - b. Return to work at 6 weeks after randomization.
5. **Electrodiagnostics (EDX)** at 3 months and 9 months after randomization.
6. **Patient-reported outcome measures:** health-related quality of life (EQ5D-5L) at 6 weeks, 3 months, 6 months, 9 months and 18 months after randomization. Patient-reported outcome measurements will also be assessed after 10 days in the surgical arm of the trial.

For all secondary endpoints, baseline measurements will be obtained if applicable.

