#### **8.7.15 Work Productivity and Activity Impairment Questionnaire: General Health (WPAI:GH)**

Health economic aspects of foot drop will be evaluated through the Work Productivity and Activity Impairment Questionnaire (WPAI). The WPAI is widely used and validated in multiple languages. The WPAI allows for assessment of employment and professional productivity among other features. Participants will fill in the WPAI at baseline, 6 weeks and 6 months. WPAI will be available online. If the patient receives allowances, the amount will be noted for economic analysis. This is not considered standard of care. The English version of the WPAI is included in Appendix 7.

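### The societal analysis is set at 18 months, but productivity is measured only to 6 months, leaving the last 12 of 18 months (67%) without work-loss data, including the whole period of permitted cross-over

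*Protocol*

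**What the plan says.** Section 11.5 of the protocol fixes three elements of the economic evaluation.

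- Horizon: "The time horizon of the economic evaluation is 18 months".
- Perspective: "The economic evaluation will be conducted from a healthcare payer (base case) and societal perspective".
- Productivity as a cost: "Indirect costs include absenteeism from paid and unpaid work and presentism".

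The same section fixes how work-related data are gathered: "The WPAI will be collected at baseline, 6 weeks and 6 months", and "Return to work will be assessed six weeks after randomization". Section 8.7.15 agrees ("Participants will fill in the WPAI at baseline, 6 weeks and 6 months"), as do the endpoint list in section 4.3.2 ("Work productivity and Activity Impairment Questionnaire at 6 weeks and 6 months after randomization") and the table in section 8.8. Section 5.1 confirms that the gap at the last visit is intended: all primary and secondary endpoints, "with the exception of electrodiagnostics, WPAI and return to work, will be assessed at 18 months".

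The EQ-5D-5L, by contrast, is collected through to 18 months. Sections 5.1 and 8.9 permit cross-over from conservative treatment to surgery once the 9-month assessment is done. Section 14.9 describes the planned data linkage as a source of health-care costs and does not mention productivity.

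**The concern.** The stated perspective and horizon need productivity costs up to month 18, and the data collection stops supplying them at month 6. The unmeasured stretch is not a quiet tail: it contains the period in which patients in the conservative arm may have surgery. The linkage should pick up the cost of that surgery, and the EQ-5D-5L should reflect its effect on quality of life at 18 months. Nothing named in the protocol would pick up the work lost while recovering from it, or the work regained because of it.

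An 18-month societal cost-effectiveness ratio would then combine health-care costs and quality of life followed to 18 months with productivity values carried forward from a single week around month 6. Work matters to these patients: sections 2 and 14.2 report that occupation was the most frequent reason interviewed patients gave for declining to take part.

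**Working it through.** The protocol gives no coverage figure of its own to reproduce. The check is a comparison of schedules.

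**Inputs**
- Horizon: 18 months (section 11.5).
- Last WPAI: 6 months (sections 4.3.2, 8.7.15, 8.8 and 11.5), with a visit window of plus 2 weeks (section 8.8).
- Return to work: 6 weeks only (sections 8.7.16 and 11.5).
- Earliest permitted cross-over: after the 9-month assessment (sections 5.1 and 8.9).
- WPAI recall for hours missed: the past seven days (Appendix 7).

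**Step 1. Share of the horizon after the last productivity measurement**
(horizon − last WPAI) / horizon = (18 − 6) / 18 = 12 / 18 = 67%.

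**Step 2. Does the visit window change this?**
18 months = 18 × 365.25 / 12 = 547.9 days. The latest 6-month visit falls at 6 × 365.25 / 12 + 14 = 196.6 days. The share is (547.9 − 196.6) / 547.9 = 64%, so the answer barely moves.

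**Step 3. Where does permitted cross-over fall?**
Months 9 to 18 make up (18 − 9) / 18 = 50% of the horizon. Month 9 is later than month 6, so all of this period lies after the last WPAI.

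**Step 4. Is there another source after month 6?**
Return to work ends at 6 weeks. The linkage is described as covering health-care costs. Section 8.7.15 has the amount of any allowances noted, but ties this to the WPAI, which ends at 6 months. No other source is named.

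**Step 5. Would the WPAI alone at 9 and 18 months close the gap?**
Not for absence after cross-over surgery. The 9-month form looks back over a week before cross-over is permitted, and the 18-month form sees only the final week. Months 9 to 18 last 9 × 365.25 / 12 / 7 = 39.1 weeks, so one recalled week is 1 / 39.1 = 2.6% of them. Time off after an operation in month 10 or 12, for example, would normally be missed. An item covering the whole interval since the last visit is needed.

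**The case against.** The strongest defence is that the schedule is deliberate. Sections 8.7.16 and 11.5 reason that return to work after improvement generally lasts and that relapse is not expected in most cases. Section 14.2 shows that burden was weighed: patients were divided on the WPAI, and the SF-36 was dropped after feedback about too many questionnaires. Sections 11.4.6 and 11.5 place the economic analysis in a separate plan, and section 11.5 foresees sensitivity analyses on cost assumptions.

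Part of this stands. The durability argument is reasonable for patients who have recovered by month 6. It does not cover those who have not, who are the likely candidates for later surgery; section 8.7.16 itself recognises that some patients will not recover enough to resume their former work. A separate plan and sensitivity analyses can vary assumptions, but they cannot supply observations.

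A reader might infer four stronger points that the protocol does not support.
- **That the whole economic evaluation is compromised.** The base case is the payer perspective. It rests on linked health-care costs and on an EQ-5D-5L collected to 18 months, and neither is touched.
- **That no cross-over surgery is covered.** This holds only for permitted cross-over. Sections 11.4.1 and 11.4.3 foresee surgery in the conservative arm before 9 months, and some of it could precede the 6-month WPAI.
- **That work is observed in only three single weeks.** Sections 8.6 and 8.7.16 also record the last working day and ask patients to note the date of return to work, reported at 6 weeks. This gives information on absence up to that visit.
- **That the result is biased towards one arm by a known amount.** Nothing in the protocol allows the direction or size of any bias to be worked out.

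**Conclusion.** The mismatch is real and confined to the societal perspective. Productivity is unmeasured for 12 of the 18 months (67%, or 64% if the 6-month visit falls at the end of its window), including the whole period of permitted cross-over. The 67% treats the first 6 months as covered, which is generous to the plan given the seven-day recall. The conclusion assumes that no work-loss source beyond those named in the protocol is planned. As written, the trial can support an 18-month result from the payer perspective. It can support a societal result based on measured productivity only to 6 months. The clinical endpoints and the quality-adjusted life-years are unaffected.

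**What to change.** Choose one of two changes.

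**(a) Collect the data.** Add the online WPAI at the existing 9- and 18-month contacts, next to the EQ-5D-5L, together with a short item on dates or days off work since the last visit. Amend sections 4.3.2, 5.1, 8.7.15, 8.8 and 11.5, and align the trial summary. The cost is two extra six-question forms plus one short item per patient. This is a small burden, but a real one given the pilot feedback. It is time-critical, since visits already past cannot be recovered.

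**(b) Narrow the claim.** State in section 11.5 that productivity costs and the societal result cover 6 months only, that the 18-month result is from the healthcare-payer perspective, and that any societal extrapolation beyond 6 months is a labelled sensitivity analysis with its assumption stated. This costs only wording, but gives up a societal result based on measured productivity for the cross-over period.
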